7.7 Early Termination Visit

The Early Termination Visit will occur if a subject is not able to complete the study procedures as detailed in the protocol for any reason. The schedule of events for the Early Termination Visit is identical to the Final Study Visit (See Section 7.6).

- Confirm that the morning dose of replacement steroids (GC/MC) was not taken or if taken confirm the day and time of the last dose
Note: If the morning dose of replacement steroids (GC/MC) was taken, it is acceptable to complete the Final Study Visit
- Confirm the day and time of the last dose of IMP
- Perform drug accountability and confirm compliance with IMP
- Review of concomitant medication

- Assess AEs
- Complete physical examination
- Vital signs (including blood pressure, pulse, respiration, body weight and temperature)
- 12-lead ECG
- Blood sampling for hematology, serum chemistry, PT/aPTT/INR
- Urinalysis
- Urine pregnancy testing (β -hCG) for females who are not surgically sterile or who have not been naturally postmenopausal for at least 12 consecutive months (i.e., who have had menses any time in the preceding 12 consecutive months)
- **Blood sampling for steroids/steroid intermediates (before 10 AM)**
- Blood sampling for exogenous glucocorticoid levels
- Blood sampling for ATR-101 PK assessment (trough levels)

7.8 Follow-up Visit

Two weeks after completion of the Final Study Visit or Early Termination Visit, the PI, SI or other qualified medical personnel from the study center will contact the subject. A telephone interview will take place to confirm the status of the subject. Any safety events will be reported and concomitant medications, including replacement steroids will be recorded. This telephone interview will conclude the subject's study participation.

8 QUALITY CONTROL AND ASSURANCE

Before any subjects can be enrolled at an investigational site and prior to the conduct of any protocol-specific procedures, formal training of investigational site personnel will be conducted. The PI/SI and all relevant investigational site staff are to be trained on all aspects of the trial for which they are responsible. Site personnel may be trained at a formal initiation visit, at an Investigator's Meeting, or by another means as necessary. Monitoring and auditing procedures will be conducted in compliance with the International Conference on Harmonisation (ICH) Guidelines for Good Clinical Practice (GCP). Onsite verification of the eCRFs for completeness and clarity, crosschecking with source documents, and clarification of administrative matters will be performed on a regular basis. The investigational site will be monitored immediately following enrollment of the first subject at the site (i.e., within approximately 2 weeks) to verify that inclusion/exclusion criteria have been fulfilled. Subsequent monitoring visits will occur at regular intervals as noted in the monitoring plan. Through frequent communications with the investigational site, the CRA will ensure that the investigation is conducted according to protocol design and all applicable regulatory requirements. Additional details on the monitoring of this clinical trial are provided in Section 10.5. During the course of the clinical trial, investigational sites, the clinical trial database, and all associated clinical trial documentation may be subject to quality assurance audits by the Sponsor, or their appointed representatives, on a planned or as-needed basis. In addition, representatives of associated regulatory bodies may conduct inspections at their discretion. The Investigator is responsible for ensuring direct access to all protocol-specific materials for the purpose of these activities.

9 PLANNED STATISTICAL METHODS

9.1 General Considerations

Sample size considerations are based on a Simon 2-stage Minimax design with 1-sided alpha of 5% and 80% power.

Stage 1 consists of 9 completed subjects. The study will stop at Stage 1 if either of the following conditions are met:

- Futility criteria: defined as ≤ 2 of 9 (22%) subjects meeting the primary outcome measure (17-OHP $\leq 2 \times$ ULN)
- Success criteria: defined as ≥ 7 of 9 (78%) subjects meeting the primary outcome measure (17-OHP $\leq 2 \times$ ULN)

Stage 2 will commence if 3, 4, 5 or 6 of the 9 subjects meet the primary outcome measure. In this scenario, accrual will continue with up to 8 additional subjects for a total of no more than 17 subjects. Accrual may stop earlier with sufficient evidence for further development if a total of 7 or more subjects respond (minimum observed response rate of 7/17, 41%).

The study medical monitor along with the Sponsor may determine if a subject will be replaced in order to have a minimum of 9 evaluable subjects for Stage 1. Possible reasons for replacement may be due to extreme noncompliance with IMP not related to an adverse event, noncompliance with the protocol such as the use of prohibited medications that could confound results.

9.2 Analysis Populations

An intent to treat population is not deemed necessary for this study given the relatively small number of subjects.

The per protocol population will include all subjects that have taken at least 11 days of ATR-101 treatment at Dose Level 1 (the lowest dose level) and have at least one post-baseline efficacy assessment (i.e. 17-OHP) without having a significant protocol deviation.

The safety population will include all subjects that received at least one dose of IMP.

9.3 Patient Demographics and Baseline Characteristics

Demographic and clinical characteristics of subjects enrolled onto this study will be summarized. For categorical variables, frequencies and percentages will be provided. Means with standard deviations or medians/percentiles will summarize non-categorical variables.

9.4 Treatment

A frequency distribution will be generated for the dose levels administered. Any deviations to the dose escalation criteria will also be noted.

9.5 Primary Efficacy Endpoint

The primary efficacy endpoint will be the percentage of responders. **A responder is defined as a subject that meets the primary outcome measure of 17-OHP ≤ 2 x ULN at any dose level.** Subjects will enter the study with 17-OHP ≥ 4 x ULN. The 17-OHP level associated with the primary outcome measure is aligned to clinical management practices for classic CAH.

9.6 Secondary Endpoints

Descriptive statistics and graphical summaries within each cohort, and for each dose as appropriate, will be utilized to present the pharmacokinetic and pharmacodynamics parameters assessed.

9.7 Safety

Safety parameters, including adverse events, treatment discontinuations, laboratory changes and abnormalities, and changes in ECG parameters will be tabulated and each dose, as appropriate.

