5.3.3 Changes in Daily Dose are Not Permitted

Subjects must adhere to the daily dose of IMP according to each dose level. Deviation from the protocol regimen is not permitted. Specifically, lower daily doses are not permitted for any reason. If a subject cannot tolerate a given dose due to a safety issue then early termination from the study is the recommended course of action. Decreasing to a lower dose (e.g., once per day dosing or taking fewer tablets at each AM or PM dose) or to the previous dose level is not permitted. Additionally, increased doses are not permitted at any time other than those associated with the protocol design (i.e. advancing to the next dose level). Taking more tablets at a given dose is not permitted under any circumstances.

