5.3.5 Withholding IMP

A “drug holiday” or “dosing break” is not recommended due to the relatively short 28 day period per dose level. However, withholding IMP may be possible under specific conditions. For example, a subject may have a medical event (e.g., dental emergency) that is considered to be transient or reversible within a few days that may potentially have a preferred outcome by withholding IMP. Depending on the specific circumstances, additional days of dosing may be possible to complete a 14 day dosing cycle. The PI or SI should discuss potential events of this nature with the study medical monitor and Sponsor prior to the event if at all possible.

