6 STUDY PROCEDURES

6.1 Allowable Variation in Study Visits

Visits and the protocol defined days for each specific period/procedure should be adhered to as much as possible. However, there is flexibility to allow for logistical considerations and to accommodate scheduling conflicts. Variations to the protocol defined visit dates (i.e. study days) may be allowed depending upon the specific circumstances.

- Screening Visit. Up to 21 days.
- Baseline Lead-in Period. A minimum of 14 days must be completed but an additional 3 days beyond the 14 day period is allowed.
- Dose Levels 1-5
 - ATR-101 Treatment Period
 - A minimum of 11 days (22 doses) of ATR-101 must be taken prior to drawing blood samples for an assessment of efficacy and safety. Therefore, sample collection cannot occur earlier than the 12th day of dosing for a given dose level.
 - A maximum of + 3 days is allowed beyond the scheduled 14 day ATR-101 treatment period.
 - Placebo Washout Period
 - A minimum of 11 days (22 doses) of placebo must be taken prior to drawing blood samples for an assessment of efficacy and safety. Therefore, sample collection cannot occur earlier than the 12th day of dosing for a given dose level.
 - A maximum of + 3 days is allowed beyond the scheduled 14 day placebo treatment period.
- Follow-up visit. A window of ± 3 days is permitted.

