## **6.4 Subject Disposition**

Counts of subjects in each population, as well as counts and percentages of subjects who completed the study and who withdraw early from the study, with the reason for early withdrawal, will be presented by ATR-101 dose level and overall.

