### **6.11.1 Adverse Events**

AEs will be coded and classified by system organ class and preferred term using the Medical Dictionary for Regulatory Activities (MedDRA). All AEs reported for enrolled subjects during the clinical study will be recorded on the electronic case report form (eCRF). All AEs, regardless of relationship to study drug or procedure, should be collected beginning from the time the subject signs the study consent. AEs in clinical investigation subjects include any change in the subject's condition. This includes symptoms, physical findings, or clinical syndromes.

TEAEs are defined as adverse events that happen for the first time on or after the first dose date (Dose Level 1 Day 1) of ATR-101.

An overview with counts of events and subjects will be provided by dose level and treatment at AE onset and overall for the incidence of AEs in the following categories:

- Any TEAE
- Maximum severity of TEAE
- Any study drug related TEAE
- Maximum severity of study drug related TEAE
- Any serious treatment-emergent SAE (TESAE)
- Any study drug related SAE
- Death due to AE
- AE leading to discontinuation from study
- Study drug related AE leading to discontinuation from study

The incidence of TEAEs will be summarized by dose level and treatment at AE onset and overall by system organ class and preferred term. System organ class will be sorted alphabetically and preferred term will be sorted by descending total frequency within system organ class. Similar summaries will be provided for TEAEs by maximum severity. The same summaries will be done for study drug related TEAEs.

The AE summaries will be provided by dose level and treatment at AE onset. In other words, AEs starting on or after ATR-101 and prior to the subsequent Placebo dose will be attributed

to ATR-101. AEs starting on or after Placebo and prior to the subsequent ATR-101 dose will be attributed to Placebo.

Listings will be provided for any SAEs, AEs leading to discontinuation from study, and AEs beginning in the Placebo Baseline Lead-In Period.

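### Protocol 9.7 names treatment discontinuations, but the SAP counts only discontinuation from the study, so no planned table links an AE to ATR-101 stopped early or withheld in a subject who still completes.

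*Protocol*

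**What the plan says.** Protocol 9.7 gives the safety outputs: "Safety parameters, including adverse events, treatment discontinuations, laboratory changes and abnormalities, and changes in ECG parameters will be tabulated and each dose". The sentence closes by making the tabulation for each dose a matter of what is appropriate.

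SAP 6.11.1 turns this into tables: "An overview with counts of events and subjects will be provided by dose level and treatment at AE onset and overall". The only categories there concerning discontinuation are "AE leading to discontinuation from study" and "Study drug related AE leading to discontinuation from study". SAP 6.4 plans a disposition table for those "who completed the study and who withdraw early from the study, with the reason for early withdrawal, will be presented by ATR-101 dose level". SAP 7, which records departures from the planned analysis, covers only the Stage 1 stopping criteria.

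Three protocol rules bear on whether stopping the drug and leaving the study are the same event:

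- For a subject who cannot tolerate a dose, Protocol 5.3.3 says that "early termination from the study is the recommended course of action".
- Protocol 5.3.5 says that "withholding IMP may be possible under specific conditions", with dosing days possibly added afterwards.
- Protocol 6.1 accepts a short course: "A minimum of 11 days (22 doses) of ATR-101 must be taken prior to drawing blood samples".

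**The concern.** Safety is part of the primary objective (Protocol 2.1, SAP 3.1), and tolerability by dose level is a main product of a five-level escalation. Stopping the drug because of an AE is a direct measure of tolerability. The protocol names that event; the SAP replaces it with leaving the study and does not say so.

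Elsewhere the protocol keeps the two apart. Section 6.12.1 lists withdrawing and withholding study treatment as separate actions, the title of 6.15 distinguishes the study from the study drug, and 10.3 lets a subject give up IMP, consent, or both. If a subject stops ATR-101 for an AE and still completes, the report would show an AE in one table and perhaps a short course in another, with nothing to say that one caused the other.

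**Working it through.** The plan gives no figure to reproduce. The check compares the texts and then asks whether the exposure tables fill the gap.

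**1. Event named against event counted.**

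| Source | Event |
|---|---|
| Protocol 9.7 | discontinuation of treatment |
| SAP 6.11.1 | AE leading to discontinuation from the study |
| SAP 6.4 | early withdrawal from the study, with reason |
| SAP 6.7 | ATR-101 duration, tablets and compliance, without reasons |
| SAP 7 | no mention of the change |

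**2. Can a subject stop ATR-101 early and still complete?** The rules allow it. Under Protocol 6.1 the efficacy sample is valid once 11 days have been taken, so up to 3 of 14 days (3/14 = 21.4%) can be lost within the visit window. After washout, a subject with Day 15 17-OHP ≤ 2 × ULN goes to the Final Study Visit (Protocol 7.4). At Dose Level 5 every subject does, whatever the Day 15 value (Protocol 7.5). Withholding and resuming under 5.3.5 also leaves the subject in the study.

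**3. Do the SAP 6.7 tables show it?** The formulas for Dose Levels 1–3 are:

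- duration = last dose date − first dose date + 1
- compliance = 100 × tablets administered / (duration × 2)

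For a nominal 14-day course at one tablet BID:

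| Course | Tablets | Duration (days) | Compliance |
|---|---|---|---|
| Full | 28 | 14 | 28/28 = 100% |
| Stopped after day 11 | 22 | 11 | 22/22 = 100% |
| Stopped after day 7 (formula check only) | 14 | 7 | 14/14 = 100% |
| Withheld 2 days, ended day 14 | 24 | 14 | 24/28 = 85.7% |
| Withheld 3 days, ended day 14 | 22 | 14 | 22/28 = 78.6% |
| Withheld 3 days, extended to day 17 | 28 | 17 | 28/34 = 82.4% |

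An early stop leaves compliance at 100%, because numerator and denominator shrink together. It shows only as a shorter duration, where a stop for an AE looks the same as a visit booked early. An interruption falls below the 80% line only in the fifth row, and again no reason is attached.

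**4. Missing dates.** If the last dose date within a level is missing, SAP 6.7 uses the day before the next level starts. Read literally for ATR-101, that is nominally day 28. A course stopped on day 7 would then show a 28-day duration and 14/(28 × 2) = 25% compliance: the short course disappears from the duration summary and reappears as apparent non-compliance.

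**5. Dose attribution.** The SAP 6.11.1 overview is indexed by level and treatment at AE onset. An AE that begins at one level and leads to a stop at a higher one would be counted at the lower.

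**6. Scale.** One subject is 1/9 = 11.1% at Stage 1 or 1/17 = 5.9% at full size. This is the weight of a single case, not an estimate of frequency.

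**The case against.** The strongest reply is that stopping treatment and leaving the study largely coincide in this protocol. Dose reduction is not allowed, early termination is the recommended response to intolerance (5.3.3), 6.15 gives one list of reasons for removal and sends those subjects to a Final or Early Termination Visit, and 7.7 applies the Early Termination Visit broadly. On that view the study-level rows are a reasonable working form of Protocol 9.7. This stands for most true discontinuations. It does not cover a short course within the 6.1 window in a subject who completes, and 5.3.3 recommends rather than requires leaving.

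A second reply is that 9.7 speaks of discontinuations and qualifies the split by dose. Withholding and resuming is an interruption, so 9.7 does not require it to be tabulated. That is correct; an interruption row would go beyond the protocol.

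A third is that table and listing layouts are in a separate document (SAP 8), so a listing may show the action taken with study drug. That is possible, but a listing would not supply the tabulation that 9.7 describes.

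A reader might infer that such an event vanishes from safety reporting altogether. It does not: the AE is counted in the TEAE tables by severity and relatedness, and a short course lowers the duration summary. A reader might also infer that tolerability will look better at the dose where response occurs, since responders complete at that level. The documents give no frequency and no reason to expect AE-driven short courses to cluster in responders. The 6.1 window is offered for logistics and scheduling, and whether a site would record such a subject as a completer is not stated.

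**Conclusion.** The point holds in a limited form. The SAP counts a narrower event than Protocol 9.7 names, and SAP 7 does not record the difference. No planned table connects an AE with ATR-101 being stopped early or withheld in a subject who still completes, and the compliance table reads 100% for an early stop. The gap is confined to interruptions and to early stops without early termination. It changes no endpoint, sample size, error rate or stopping rule, and safety analysis is descriptive throughout.

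The conclusion assumes that a subject who stops early within the 6.1 window and attends the Final Study Visit is recorded as a completer. No claim is made about how often this happens or in whom. It is worth correcting because one subject carries 5.9% to 11.1% of the sample and the correction is cheap.

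**What to change.** - In the SAP 6.11.1 overview, add *AE leading to discontinuation of ATR-101*, counted at the dose level being taken when the drug was stopped. This brings the SAP into line with Protocol 9.7.
- As a low-cost addition beyond 9.7, add *AE leading to interruption of ATR-101*, counted in the same way.
- In SAP 6.4, add the number of subjects per dose level who stopped ATR-101 early, with the reason.
- If the sponsor prefers to keep the present tables, state in SAP 7 that treatment discontinuation is read as study discontinuation, and why. This records the change but leaves the gap open.

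The cost is two rows and one disposition line. The dosing dates are already used in SAP 6.7. The rows also need the AE record to hold the action taken with study drug, which the documents do not confirm; if it does not, the link has to come from the reason recorded for the stop. The downside is slightly longer tables and a possibly less favourable tolerability count.

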9.8 Pharmacokinetic and Pharmacodynamic Analyses

Pharmacokinetic (PK) assessments will be performed at each dose level to determine ATR-101 exposures and to profile PK/PD relationships. PK assessments will include C_{max} , Area Under the Curve ($AUC_{0-4 \text{ hr}}$), and trough levels.

Individual subject PK data will be analyzed along with pooling of subjects' data at each dose level.

PK/PD analyses will be detailed in the Statistical Analysis Plan.

9.9 Interim Analysis

No interim analysis is planned for this study as neither the efficacy nor the safety results will be blinded to the PI/SI, study medical monitor or the Sponsor.

10 ADMINISTRATIVE CONSIDERATIONS

10.1 Institutional Review Board (IRB)/Independent Ethics Committee (IEC)

Prior to initiation of the study at each investigational site, the protocol, the informed consent form(s), the subject information sheet(s), details of the subject recruitment procedures, and any other relevant study documentation will be submitted to the responsible local and/or national IRB/IEC. A letter from the IRB/IEC indicating approval of the Investigator and study site must be submitted to the study Sponsor. All reviews and approval by the IRB/IEC will be in accordance with Title 21 of the Code of Federal Regulations (CFR), Part 56.

The PI/SI will promptly report any new information that may adversely affect the safety of subjects or the conduct of the study to the IRB/IEC. Similarly, the PI/SI will submit written summaries of the study status to the IRB/IEC annually, or more frequently if requested. Upon completion of the study, the Investigator will provide the IRB/IEC with a brief report of the outcome of the study, if required.

10.2 Ethical Conduct of the Study

The guidelines of the World Medical Association Declaration of Helsinki in its revised edition (48th General Assembly, Somerset West, Republic of South Africa, October 1996), the guidelines of ICH GCP (CPMP/ICH/135/95), as well as the demands of national drug and data protection laws and other applicable regulatory requirements, will be strictly followed.

10.3 Subject Information and Consent

The PI/SI is responsible for ensuring that subjects do not undergo any study-related examination or activity before giving informed consent. The subject must give written consent after the receipt of detailed information regarding the study. The verbal explanation will cover all the elements specified in the written information provided to the subject. If the written informed consent is provided by the legal guardian because the subject is unable to do so, a written or verbal assent from the subject must also be obtained.

The PI/SI will inform the subject of the aims, methods, anticipated benefits, and potential hazards of the study, including any discomfort it may entail. The subject must be given every opportunity to clarify any points he/she does not understand and must be provided with more information if requested. At the end of the interview, the subject may be given time to reflect and can request more time if needed. The subject and/or legal guardian will be required to sign and date the informed consent form. After completion, informed consent forms will be kept and archived by the PI in the PI study file.

It should be emphasized to the subject that he or she is at liberty to either discontinue IMP and/or withdraw consent to participate at any time, without penalty or loss of benefits to which he or she is otherwise entitled. Subjects who refuse to give or withdraw written informed consent may not be included or continued in this study, but this will not affect their subsequent care.

Please refer to Title 21 of the CFR, Part 50 – Protection of Human Subjects for specific details on this regulation.

